7.1.1 Analytical Populations

- **Intent-to-Treat:** The ITT population will include all randomized subjects. All primary and secondary efficacy analyses are to be on the ITT population.
- **Modified Intent-to-Treat:** The mITT population will include all randomized subjects with at least one post-baseline primary outcome assessment. Results of the efficacy analyses based on the mITT population will be presented as a sensitivity analysis. Treatment assignments in the mITT population will be based on the treatment to which the subject was randomized.
- **Safety:** The safety population will include all randomized subjects who received the study drug. Treatment assignments in the safety population will be based on the treatment that was received (if different from the randomized treatment).
- **Per-Protocol:** The PP population will exclude from mITT population those subjects who have major protocol violations. Major protocol violations include violation of entry criteria, receiving the incorrect randomization, noncompliance with study drug administration (missing the study drug administration more than 80% of study drug or failure to apply the study drug for at least 5 days per week and miss more than 2 of 7 days of application), and the use of prohibited medications. Treatment assignments in the PP population will be based on the treatment that was received (if different from the randomized treatment).

7.1.2 Analysis of Subject Disposition

Disposition will be summarized for subjects enrolled into the study. For the subjects who are enrolled, summaries will be presented for the number and percentage of subjects who completed the study and for those who prematurely withdrew. The reason for withdrawal will be summarized by number and percent for subjects who prematurely withdrew. Visit attendance will be summarized for all enrolled subjects.

A list of subjects with protocol violations and their specific violations will also be provided. A separate listing will indicate all mis-assignments or out of sequence assignments of study drug according to the randomization code list and the reason for the error.

7.1.3 Analysis of Demographic and Background Characteristics

The demographic data will be summarized for the ITT population. Demographic data (age, gender, ethnicity, race, iris color, chalazion onset, chalazion erythema score at baseline) will be presented for each group (SUN-131 1.5% TDS and placebo TDS), and for all enrolled subjects combined. Baseline medical history will be summarized and a subject listing will be provided. A summary of all prior and concomitant medications will be presented in tabular form by therapeutic drug class and generic drug name using the World Health Organization (WHO) Drug classification. A summary of all prior and concomitant therapy will be summarized. Ocular and non-ocular medical histories will be presented in Appendices.

7.1.4 Analysis of Study Medication Compliance and Exposure

Study medication compliance entails wearing the study drug for minimum of 16 hours and maximum of 24 hours each day for 14 days. Compliance will be assessed through Visit 3 by patch adhesion assessments carried out by the investigator, by subject diaries and by collection of all used and unused study drug. The patch adhesion scores and their changes from baseline will be summarized by treatment group using descriptive statistics (number of subjects, mean, median, range, and standard deviation). Exposure of the study will be summarized by treatment group using descriptive statistics (number of subjects, number of study drug applied, number of days applied, number of hours applied, mean, median, and standard deviation).

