4.1.3 Removal of Subjects from Treatment or Assessment

Subjects may withdraw their consent to participate in this study at any time without prejudice. The investigator must withdraw from the study any subject who requests to be withdrawn. **The medical monitor must be notified of all subject withdrawals within 24 hours by telephone or email.**

In addition, the investigator may withdraw a subject from the study for any of the following reasons:

- A protocol violation occurs,
- The subject is lost to follow-up,
- A serious or intolerable AE occurs, or
- The sponsor or investigator terminates the study.

The sponsor may withdraw a subject for noncompliance with use of study medication if they do not apply the study drug for a minimum of 16 hours and a maximum of 24 hours for at least 80% of the time required (or at least 5 days per week) and miss more than 2 of 7 days of application in the trial. Senju also reserves the right to discontinue the study at any time for either clinical or administrative reasons.

If a subject fails to return for scheduled visits, a documented effort must be made to determine the reason. If the subject cannot be reached by telephone after 2 attempts, a certified letter should be sent to the subject (or the subject's legally authorized representative, if appropriate) requesting contact with the investigator. Attempts to contact the subject should be documented in the study records.

Prior to enrollment into the study, the investigator or designee must explain to each subject that the subject's protected health information obtained during the study may be shared with the study sponsor, regulatory agencies, and the IRB or EC in order to analyze and evaluate study results. It is the investigator's (or designee's) responsibility to obtain written permission to use protected health information per country-specific regulations. If permission to use protected health information is withdrawn, it is the investigator's responsibility to obtain a written request, as well as to ensure that no further data will be collected from the subject and the subject will be removed from the study.

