4.7 Treatment Compliance

In this study, treatment will consist of wearing a total of 14 study drug for a minimum of 16 hours and maximum of 24 hours each day for 14 days. On Days 8 ± 1 and 15 ± 1 , the study drug should not be replaced with a new study drug in the morning of the visit to ensure the study drug is worn for a minimum of 12 hours before removal by the investigator at the site. The subject may wear the study drug over 24 hours on these visit days if necessary. On Day 8 ± 1 , subjects should apply a new study drug after completion of evaluations to ensure the study drug is worn for a minimum of 16 hours on that day. The subject can then return to their normal schedule of study drug removal and replacement. Subjects will record the time of application and time of removal of each study drug daily, any mis-application and fall-off as well as any unusual events in the electronic subject diary. Treatment compliance will also be assessed based on a subject diary, and all used and unused study drug returned at each visit. [REDACTED]

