7 STATISTICAL METHODS AND DETERMINATION OF SAMPLE SIZE

7.1 Statistical and Analytical Plans

All data collected on CRFs will be presented in data listings. The primary and secondary endpoints for this trial will be evaluated using the Intent-to-Treat (ITT) population with the Modified Intent-to-Treat (mITT) performed as a sensitivity analysis. The safety analyses will be carried out using the safety population. Comfort scores (ocular, skin, and the average of both), patch adhesion, and residual drug content will be analyzed using the ITT population (and mITT and Per-Protocol [PP] populations if there are subjects with protocol deviations or incomplete data). In general, the grade for each measure in each eye will be used for analysis of treatment effects unless otherwise specified. All analyses will be conducted in a validated instance of SAS 9.1 or higher.

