7.1.5.2 Key Secondary Analyses

7.1.5.3 Other Efficacy Analyses

All quantitative secondary endpoints will be analyzed using the two-sample t-test (parametric) and the Wilcoxon-Mann-Whitney test (nonparametric). Secondary endpoints that are defined as time-to-event variables will be summarized using the Kaplan-Meier method; the log-rank test will be used to compare the distributions in the 2 groups. The primary and secondary endpoints will also be analyzed in the PP population. All secondary analyses will be conducted using two-sided tests at the $\alpha = 0.05$ level of significance.

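### As printed, the per-protocol noncompliance rule counts missed patches but not hours of wear, so a subject with half the minimum wear can stay in the per-protocol set

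*Combined protocol and SAP*

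**What the plan says.** Section 7.1.4 sets the standard: "Study medication compliance entails wearing the study drug for minimum of 16 hours and maximum of 24 hours each day for 14 days". The same section lists "number of days applied, number of hours applied" as separate exposure summaries.

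Section 7.1.1 removes subjects with major violations from PP. The list opens "Major protocol violations include violation of entry criteria" and goes on to noncompliance with administration, which it explains in brackets. One limb is missing more than 80% of study drug. The other is "failure to apply the study drug for at least 5 days per week and miss more than 2 of 7 days of application". Neither mentions hours.

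Section 4.1.3 has a similar rule for withdrawal. The sponsor may withdraw subjects who "do not apply the study drug for a minimum of 16 hours and a maximum of 24 hours" for at least 80% of the required time (or at least 5 days per week) *and* who miss more than 2 of 7 days.

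The data for an hours rule are collected. Section 4.7 states: "Subjects will record the time of application and time of removal of each study drug daily". That section ends in blacked-out text.

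On use, 7.1 makes ITT the main population, "with the Modified Intent-to-Treat (mITT) performed as a sensitivity analysis". Section 7.1.5.3 adds: "The primary and secondary endpoints will also be analyzed in the PP population".

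**The concern.** A PP analysis is meant to show the effect in subjects who used the treatment as planned. Here the plan has one meaning of compliance for reporting (hours per day) and another for deciding who belongs in PP (patches and days). Because 7.1.4 treats days and hours of application as two different summaries, a programmer following 7.1.1 would naturally derive days applied without looking at wear time. Subjects who put on every patch but took it off early would then count as fully compliant for PP, and the PP estimates for the primary and secondary endpoints would not describe treatment as planned.

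**Working it through.** The plan gives no figure to reproduce here. The check compares the rules and applies them to example subjects.

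**Inputs**
- Planned treatment: 14 patches, one per day for 14 days (4.7).
- Minimum wear: 16 h per day (7.1.4).
- PP exclusion for noncompliance: more than 80% of study drug missed, or fewer than 5 application days per week with more than 2 of 7 days missed (7.1.1).
- Wear of 8 h per patch: my illustration, not a figure from the documents. It is below the planned wear in the earlier repeated-dose studies: 16 ± 2 h in Phase 1 Part 2 (14 to 18 h) and 16 ± 4 h in Phase 2 (12 to 20 h).

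**Rules side by side**

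| Section | Purpose | Hours in the rule? | Binding? |
|---|---|---|---|
| 7.1.4 | Compliance definition | Yes, 16 to 24 h per day | Reporting only |
| 4.1.3 | Withdrawal | Yes, joined by *and* to missed days | Optional |
| 7.1.1 | PP exclusion | None | Yes |

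**Printed PP rule**
- Minimum planned wear: 14 × 16 = 224 h.
- Subject A applies all 14 patches for 8 h: 14 × 8 = 112 h; 112/224 = 50%. The 16 h minimum is met on 0 of 14 days, but 0 of 14 applications are missed. Neither limb applies, so A stays in PP.
- Subject B also misses 2 days in each week: 10 × 8 = 80 h; 80/224 = 35.7%. Missed applications are 4/14 = 28.6%, not more than 80%, and 2 of 7 is not more than 2 of 7. B stays in PP.

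**Withdrawal rule (4.1.3)**
- 80% of 14 days is 11.2, so 12 days of adequate wear are needed. A has none and fails the hours part.
- A misses no application. Because the two parts are joined by *and*, a strict reading does not catch A. Even if it did, withdrawal is at the sponsor's discretion.

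**Rule with a wear-time definition of a day (study weeks Days 1–7 and 8–14)**
- A: no day counts as applied, so 7 of 7 days are missed in each week and A leaves PP.
- A subject with full wear who misses 2 days per week has 10/14 = 71.4% of days and stays, as under the sponsor's threshold.
- Lowest qualifying wear kept, before any tolerance: 10 × 16 = 160 h (160/224 = 71.4%). If two of those patches are visit-day patches worn 12 h, it is 8 × 16 + 2 × 12 = 152 h (67.9%).

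**The case against.** The strongest objection is that the rule may already exist. Section 4.7 is the natural place for a wear-time criterion, it restates the 16 to 24 h requirement, and its last lines are blacked out. Text lost to redaction is not missing from the plan. A reader might infer that the sponsor has no wear-time criterion for PP; the documents do not support that. They support only the statement that no visible text makes short wear a PP violation.

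Second, the list in 7.1.1 is open, and its word for noncompliance could be read together with 7.1.4, or its word for applying together with 4.1.3. That reading is possible. But the bracket in 7.1.1 gives its own explanation without hours, and an open list leaves short wearers to case-by-case judgment.

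Third, it is tempting to read 4.1.3 as proof that the sponsor treats short wear alone as disqualifying, so that 7.1.1 contradicts it. The text does not go that far: the hours are joined to missed days, and the action is optional. Section 4.1.3 shows that hours were in mind, not that they were meant to decide PP membership.

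Fourth, little depends on PP. Hours applied are summarized by arm (7.1.4) and protocol violations are listed (7.1.2), so short wear should be visible to a careful reader. This stands, and it is why the point is minor.

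**Conclusion.** The point holds as a minor one, with medium confidence. The printed PP rule is narrower than the plan's own definition of compliance and can keep a subject with 50% of the minimum wear, or 35.7% if two days a week are also missed. The conclusion assumes that 7.1.1 is applied as printed and that the blacked-out text in 4.7 does not supply the missing criterion.

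A reader might infer that the primary result is at risk. It is not: ITT is primary and mITT is the sensitivity analysis, and neither depends on this rule. If short wear lowers the active effect, keeping these subjects makes the PP difference smaller, which is conservative in a superiority trial.

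A reader might also want a count. The documents give no frequency of short wear. An assumed 5% to 20% of 260 randomized subjects would be 13 to 52 (260 × 0.05 and 260 × 0.20), but nothing in the documents supports that range. PP is also drawn from mITT and loses subjects for other violations. The number affected is unknown.

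**What to change.** If the blacked-out part of 4.7 already sets a wear-time criterion for PP, add a cross-reference to it in 7.1.1. Otherwise, before unmasking, amend 7.1.1 as follows:

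- Keep the existing threshold (5 days per week, more than 2 of 7 missed), applied by study week: Days 1–7 and Days 8–14.
- Count a day as applied only if a patch was worn at least 16 h by diary times, or at least 12 h for the patches removed at Visits 2 and 3. Without that allowance, patches worn as instructed could use up permitted days. In the second week they could use both if Visit 2 is on Day 9 and Visit 3 on Day 14 or 15 (patches from Day 8 and from Day 13 or 14).
- State a tolerance around the minimum, so that a few minutes' shortfall does not count as a missed patch.
- Report wear over 24 h, but do not make it a PP exclusion by itself.
- State how missing diary times and backup patches after a fall-off are counted, and how the second week is counted when Visit 3 is not on Day 15.

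Use the same definition in 7.1.4 and report the percentage compliant by arm. The limb on missing more than 80% of study drug is a separate matter and is left as it is here.

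The cost is wording in two sections, one extra derivation from data already collected, and a somewhat smaller PP set. ITT and mITT results do not change.

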7.1.5 Analysis of Efficacy

7.1.5.1 Primary Efficacy Analysis

The primary analysis will compare the proportions of subjects in the 2 groups who experience CR of the study chalazion on or before Day 15 \pm 1. CR is defined as the absence of any significant clinical signs of a chalazion with possible scarring or skin defects resulting from healing of the chalazion allowed. The primary analysis will be conducted using Pearson's chi-square test (two-sided) at the $\alpha = 0.05$ level of significance.

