Study Design	
This is a prospective multi-center, double-masked, randomized, placebo-controlled clinical trial. Subjects will be centrally randomly assigned in a 1:1 ratio to receive one of the following treatments in the affected eyelid:
 
SUN-131 1.5% TDS (n = 130) Placebo TDS (n = 130)
 
The randomization will be stratified by age group (<12 years, ≥12 years). All study drug will be worn for a minimum of 16 hours and a maximum of 24 hours each day for 14 days.
 
The following items will be assessed at screening/baseline and at 30 minutes to 1 hour after patch removal on Days 8 ± 1 and 15 ± 1.
 
 • Presence of a chalazion by examination (clinical assessment) • [REDACTED] • Erythema of the chalazion site itself as measured by a 5-point scale (0 = no sign of erythema, 1 = slight erythema, 2 = mild erythema, 3 = moderate erythema, 4 = severe erythema) • Pain in study eyelid and eye of the study eyelid related to chalazion as measured by Visual Analog Scale (VAS) of 100 mm 
Patient Reported Outcome (PRO) will be assessed by a self-evaluation diary of chalazion (present or absent), completed daily by the subjects from Day 1 through Day 15 ± 1.

Sample Size	Approximately 260 subjects will be randomized.
Study Population	Male or female subjects aged ≥ 6 years with a chalazion
Inclusion Criteria	
Subjects eligible to participate in the study must meet all of the following criteria:
 
 1. Subjects aged ≥ 6 years of either sex and of any race. 2. Subjects with a diagnosis of a single chalazion with visible granuloma in the study eyelid. Study eyelid may be either an upper or lower eyelid. 3. Subjects with a chalazion with the granuloma area (height x width) ≤ 36 mm² when measured by a caliper. 4. Subjects with chalazion erythema score of ≥ 1 (as graded on a 5-point scale: 0 = no erythema, 1 = slight erythema, 2 = mild erythema, 3 = moderate erythema, 4 = severe erythema). 5. Chalazion intended for study treatment present for no more than 21 days based on patient history on Day 1. 6. Normal eyelid function without active signs of eye/eyelid infection in either eye.

[figure not shown]

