3.4 Schedule of Assessments

3.4.1 Visit 1 (Screening /Baseline: Day 1)

Subjects will sign an ICF prior to any study-specific procedures (note: Standard of Care [SoC] assessments may be done prior to signing the ICF and incorporated into the study if within the allowed screening process). Where appropriate, study subjects who are < 18 years of age should assent to enroll in the study (with age of assent to be determined by the IRB and be consistent with local legal requirements). Demographics, medical and ocular history, and any concomitant medication and therapy use will be documented. The ocular history will include any previously diagnosed ophthalmic abnormalities and ocular surgeries (including laser procedures). The subject, if female, will be tested to confirm she is not pregnant using an in-house US FDA-approved home urine pregnancy test. The presence of a chalazion will be confirmed as well as the size of the chalazion, erythema of the chalazion itself, and pain related to chalazion in the study eyelid and eye of the study eyelid as part of the screening procedure. A photograph of the chalazion at baseline will also be taken prior to first study drug application. Subjects will also be trained on study drug application at baseline to confirm their ability to apply the patch at home. Training with training patches should only be conducted on the non-study eyelids. When considering enrollment of younger children, and the chalazion is on the upper eyelid, the eyelid size with the eyes closed should be evaluated and ensure that the study drug can be applied securely.

Ocular safety examinations including VA, slit-lamp biomicroscopy, and IOP measurement in both eyes, skin irritation assessment of the skin around the chalazion, size of chalazion, erythema of the chalazion itself, pain related to chalazion, and ocular/skin comfort query of the study eyelid/eye will be obtained at baseline prior to the application of the first study drug.

Concomitant medications will also be evaluated at baseline. Adverse events will be evaluated following the first study drug application on Day 1. First study drug application may be done at the site or by the subject/caregiver at home depending on the anticipated dosing schedule.

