7.1.7 Determination of Sample Size

7.1.8 Methods for Handling Missing Data

The primary endpoint is defined as CR by Day 15 \pm 1. For this endpoint, if a subject has missing data at the specified time point, but is known to be a complete responder at an earlier assessment, the subject will be defined as having CR. However, a subject whose prior status is unknown will be defined to be a non-responder. Subjects with missing data at Day 8 and Day 15 will be considered non-responders. Subjects with missing data at Day 8 but with data at Day 15 will be assigned as a responder or non-responder based on their Day 15 results. Subjects who are responders on Day 8 will be considered responders for the purposes of the trial regardless of the Day 15 evaluation.

For all time-to-event endpoints, subjects who do not achieve the endpoint will be censored at the date of their last assessment.

For quantitative secondary endpoints, missing data will not be imputed.

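### The primary complete-response test is valid but unadjusted, and may give up some power and precision that baseline data already collected could recover

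*Combined protocol and SAP*

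**What the plan says.** Section 7.1.5.1 sets the comparison ("The primary analysis will compare the proportions of subjects in the 2 groups who experience CR of the study chalazion") and names one method: "The primary analysis will be conducted using Pearson's chi-square test (two-sided", run "at the $\alpha = 0.05$ level of significance". It names no covariate, stratum, effect estimate or confidence interval. Section 7.1.1 applies it to all randomised subjects, and Section 7.1.8 counts a missing response as non-response unless an earlier response was seen. Sections 7.1 and 7.1.5.3 add only repeats in the mITT and per-protocol sets. No readable section adjusts or stratifies the response analysis.

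The baseline information is there. Section 4.1.1 makes entry depend on granuloma area (at most 36 mm²), erythema score (at least 1 on a 0 to 4 scale) and time since onset (at most 21 days, by history). Section 3.4.1 places the lesion assessments in the Day 1 screening: "The presence of a chalazion will be confirmed as well as the size of the chalazion", along with erythema. Section 4.4 randomises only subjects who meet the criteria, stratified by age group (<12, ≥12 years). Section 7.1.3 lists "chalazion onset, chalazion erythema score at baseline" for descriptive summary by arm; baseline size is not in that list.

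**The concern.** Complete response means that no significant clinical signs of the chalazion remain. Starting size, redness and age of the lesion are plausible predictors of whether it clears in two weeks. Any outcome variation they explain stays in the error term of an unadjusted test. Stratification balances age group between arms, but nothing in the design balances the state of the lesion.

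A prespecified adjusted analysis that reports a marginal difference in proportions asks the same question as the chi-square. If the variables are prognostic, it gives a narrower interval and more power from the same 260 subjects, and it accounts for chance imbalance in the variables modelled. At stake is some power and precision, not the validity of the result.

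**Working it through.** **Inputs from the documents.** The synopsis gives "Approximately 260 subjects will be randomized", split as "SUN-131 1.5% TDS (n = 130) Placebo TDS (n = 130". The test is two-sided at 0.05. All randomised subjects enter it, so n = 130 per arm.

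**Inputs that must be assumed.** The response rates and planned power are not visible: under "7.1.7 Determination of Sample Size" only the heading can be read. The share of outcome variance explained by the baseline variables (R²) is given nowhere. Both are varied below.

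**The plan's own figure.** The 260 can be neither reproduced nor faulted. With the pooled-variance formula, 130 per arm gives 80% power for 10% v 22.8%, 20% v 35.5%, 30% v 46.8%, 40% v 57.3% or 50% v 67.0%.

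**Formula check at 25% v 40%.** Power = Φ[(0.15 − 1.96·s₀)/s₁], where s₀ = √(2 × 0.325 × 0.675/n) and s₁ = √((0.25 × 0.75 + 0.40 × 0.60)/n). Adjustment is approximated by replacing n with n/(1 − R²).

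- Unadjusted, n = 130: s₀ = 0.0581, s₁ = 0.0573, z = 0.630, power 73.6%.
- R² = 0.10, n = 130/0.90 = 144.4: s₀ = 0.0551, s₁ = 0.0544, z = 0.772, power 78.0% (gain 4.4 points).
- R² = 0.18, n = 130/0.82 = 158.5: s₀ = 0.0526, s₁ = 0.0519, z = 0.903, power 81.7% (gain 8.1 points).

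**Simulation at rates near 25% v 40%.** With three baseline covariates and 1,500 trials per scenario, power rose from 73% to 78% at R² about 0.09 and from 73% to 82% at about 0.18. At R² of 0.02 to 0.03 the two analyses were equal (75.5% and 75.3%). The full proposed model, with the age stratum added, lost about 1 point at R² = 0. It gained about 1 point at 0.03, 4 at 0.09 and 9 at 0.17. Its type I error was 4.7% to 5.3%.

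**Simulation where the chi-square has 80% power.** Control rates were 20%, 30% and 50%, with three covariates and 4,000 trials per scenario. The adjusted analysis was a logistic model standardised to a risk difference, with an influence-function standard error. The ranges run across the three control rates.

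| R² | Combined odds ratio per SD | Adjusted power | Relative efficiency |
|---|---|---|---|
| 0 | 1.0 | 80% | 0.99 |
| 0.05 | 1.6–1.8 | 81–83% | 1.04–1.05 |
| 0.10 | 2.0–2.3 | 83–86% | 1.08–1.15 |
| 0.20 | 3.0–3.7 | 88–89% | 1.22–1.29 |
| 0.30 | 4.7–5.9 | 92–93% | 1.38–1.44 |

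Under the null (30% in both arms, 6,000 trials per scenario), type I error was 4.9% to 5.2% adjusted and 4.5% to 4.8% for the chi-square.

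**In subjects.** At R² = 0.10 an adjusted trial could match the unadjusted power with about 260 × 0.10 = 26 fewer subjects. Put the other way, the unadjusted test would need about 260/0.90 − 260 = 29 more to match the adjusted one.

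**The case against.** A reader might infer that the chi-square is a mistake, or that the trial is known to lose power. The documents support neither reading. A two-sided chi-square on all randomised subjects, with missing outcomes set to non-response, is a valid and transparent test of the stated question. No section reports an association between the lesion variables and response, or their baseline distribution. The Phase 2 summary in Section 1.2 covers disposition and safety only. Entry criteria narrow all three ranges and onset rests on recall, so R² may be small; at 0.05 the gain is about 2 points. The larger gains need strong predictors: R² of 0.20 takes a combined odds ratio of about 3 or more per standard deviation. All of this stands, and it limits the claim to a possible loss of unknown size.

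It is also fair that adjustment is not wholly free. The covariate forms, a missing-covariate rule and a fallback must be written down, and the chi-square needs none of them. Completeness of the covariates is likely but inferred: the Investigator Statement allows entry violations to be submitted for approval, and criterion 5 requires a limit to be met, not a day count to be recorded. The text under Section 7.1.5.2 is not visible, so a supportive adjusted analysis there cannot be ruled out.

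These points do not remove the case for adjustment. In simulation the downside was at most about 1 point of power, and type I error stayed near 5%. A reader might also treat the absence of baseline size from Section 7.1.3 as a substantive gap. It is a minor reporting matter, since size is an eligibility item and the starting value of a change-from-baseline endpoint.

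**Conclusion.** The concern holds as an efficiency point. The primary analysis ignores three lesion variables assessed before randomisation, and the age stratum used in the randomisation. It may therefore give up power and precision, by an amount that the documents do not determine. At 130 per arm and assumed rates near 25% v 40%, the gain forgone is roughly nil if the variables are not prognostic; adjusting would then cost at most about 1 point. It is about 4 to 5 points at R² near 0.10 and about 9 points at R² near 0.17 to 0.18. These figures rest on assumed rates and R², and on a simulated model whose form was correct. They say nothing about whether 260 is enough. Adjustment is a recommended improvement, not the correction of an error.

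**What to change.** Before unmasking, amend Section 7.1.5.1 as follows:

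- **Primary analysis:** a logistic model for complete response with arm, age stratum, baseline granuloma area (linear), days since onset (linear) and erythema score (linear).
- **Reported result:** the standardised marginal difference in response proportion, with an influence-function (robust) 95% confidence interval and p-value.
- **Missing covariates:** one simple rule, for example imputation of the overall mean.
- **Fallback:** the unadjusted difference if the model does not converge.
- **Sensitivity analysis:** the Pearson chi-square as now written.

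Adding baseline granuloma area to the Section 7.1.3 summary is a small reporting improvement. The cost is protocol and SAP wording plus a few lines of code, and the discipline of fixing the model form in advance. No new assessments or subjects are needed, provided that onset is recorded as a date or day count.
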